## **4 SUBJECT PARTICIPATION, DISCONTINUATION, AND WITHDRAWAL**

MCW must follow all MCW IRB requirements and policies regarding subject participation, found here:

<https://www.mcw.edu/HRPP/Policies-Procedures.htm>

### **4.1 Subject Status**

Subject statuses throughout the trial are defined as follows:

- Prescreening: preconsent (subject considering trial or study staff considering patient for the trial per institutional recruitment methods).
- Screening: period after consent, but prior to eligibility confirmation.
- Consented: consented, prior to eligibility confirmation.
- Eligible: the local investigator confirms all eligibly criteria apply.
- On study/enrolled: date eligibility is confirmed.
- On arm: date of enrollment.
- On treatment: first day treatment was given to the last day treatment was given.
- Off treatment: the last day treatment was given.
- On follow-up: from last day of treatment to the end of follow-up period.
- Off study: follow-up period completed, with no additional data gathered.
- Withdrawn: subject fully withdraws consent (i.e., refuses ALL follow-up, even survival) or is taken off study by the local principal investigator.

### **4.2 Prescreening and Screening Log**

The MCW study principal investigator regularly reviews screen failure reasons to understand barriers to accrual and consider amending eligibility criteria. Screen failures are defined as participants who were considered for the trial to participate in the clinical trial with or without consent, but are not subsequently assigned to the study intervention or enrolled in the study. MCWCC CTO will follow its SOPs regarding prescreening and screening tracking.

#### **4.3 Consent**

Investigators or their appropriate designees will identify potentially eligible subjects from their clinics, subject self-referrals, referrals from other clinicians, and/or other IRB-approved recruitment methods. No study conduct, including subject prescreening, can occur until after IRB approval.

A written, signed informed consent form (ICF) and a Health Insurance Portability and Accountability Act (HIPAA) authorization must be obtained before any study-specific assessments are initiated. A signed ICF copy will be given to the subject and a copy will be filed in the medical record (per local IRB policies and SOPs). The original will be kept on file with the study records.

#### **4.4 Eligibility Confirmation**

Study staff must adhere to MCWCC CTO SOPs regarding eligibility review/confirmation.

Subject Initials: \_\_\_\_\_ Subject Study ID: \_\_\_\_\_

#### **4.5 Eligibility Criteria**

\*No waivers of protocol eligibility will be granted.

All inclusion and exclusion criteria should be explicitly stated as applying to the subject in the source material (e.g., "The patient has been postmenopausal since 2010").

#### **4.6 Inclusion Criteria**

1. All adults (i.e.,  $\geq 18$  years old) patients with primary hyperparathyroidism who will be undergoing parathyroid surgery
2. All adults (i.e.,  $\geq 18$  years old) patients with persistent primary hyperparathyroidism after having undergone a failed prior parathyroid surgery who will be undergoing repeat parathyroid surgery
3. Ability to understand a written informed consent document, and the willingness to sign it.

#### **4.7 Exclusion Criteria**

A potential subject who meets any of the following exclusion criteria is ineligible to participate in the study.

1. Children and minors
2. Pregnant women
3. Patients with concurrent parathyroid and thyroid disease that require total thyroidectomy
4. Patients with secondary or tertiary hyperparathyroidism

*"I have reviewed all inclusion and exclusion criteria and confirm the subject is eligible."*

---

(Local Investigator Signature and Date)

---

## **4.8 Enrollment**

Subject enrollment logistics are defined as follows:

- OnCore® enrollment entry must occur within 24 hours of eligibility confirmation.
- A case/subject/sequence number is assigned in OnCore® from the MCW staff in sequence (i.e., inputted from the site staff, not generated by OnCore®).
  - Sites enter the case number according to the following template “XXX-XXX-001” or “XXX-001” (unless otherwise specified by MCW OnCore® Staff), where the “XXX” sections are abbreviations are determined by MCW OnCore® Staff, and “001” is the sequential subjects who consented to the trial at the site (e.g., the first enrolled case number would be XXX-XXX-001, but the second would be XXX-XXX-002).

## **4.9 Screening**

The screening procedures and assessments must be completed on the day of consultation for parathyroidectomy.

- Patient demographics
- Blood chemistry assessment of serum calcium, ionized calcium, parathyroid hormone (PTH) levels, and 25-OH vitamin D levels

## **Day of Parathyroidectomy**

To be completed within 30 days of the last dose of the study drug.

- Patient demographics
- Duration of surgery
- Number of frozen section analyses performed
- Frozen section and permanent histology reports of all excised tissues

## **Follow-Up Visits**

Patients will be followed for six months following parathyroidectomy. The visits will be within 5-14 days after surgery and at 6 months after surgery. The following procedures will be performed at the follow-up visit(s):

- Physical examination
- Vital signs
- Blood chemistry assessment of serum calcium, ionized calcium, parathyroid hormone (PTH) levels, and 25-OH vitamin D levels
- Concomitant medications
- History of visits to the Emergency room, hospitalization, or repeat surgery due to high calcium levels

- Documentation of postsurgical complications

### **Consent Withdrawal**

A subject may decide to withdraw from the study at any time. MCWCC CTO will follow its IRB of record's SOPs regarding consent withdrawal.

If a subject intends on withdrawing consent, staff should confirm which of the following options the subject chooses and document the discussion:

- Full consent withdrawal with no study follow-up.
- Selective consent withdrawal from interventional portion of the study, but agree to continued follow-up of associated clinical outcome information.

### **Investigator-initiated Withdrawal**

The investigator will withdraw a subject whenever continued participation is no longer in the subject's best interests. Reasons for withdrawing a subject include, but are not limited to, disease progression, the occurrence of an adverse event or a concurrent illness, a subject's request to end participation, a subject's noncompliance or simply significant uncertainty on the part of the investigator that continued participation is prudent. The reason for study withdrawal and the date the subject was removed from the study must be documented.

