### **2.2.3 Persistent hyperparathyroidism or hypercalcemia (failed parathyroidectomy)**

If blood calcium with/without parathyroid hormone (PTH) has not normalized at 1st post-operative visit, calcium and/or PTH is subsequently measured as necessary. Patient is defined to have a failed parathyroidectomy if hypercalcemia/hyperparathyroidism (defined as total blood calcium level > 10.5 mg/dL or 2.6 mmol/L, with/without elevated serum intact PTH > 65 pg/ml or 6.9 pmol/L) persists at or after the 6th postoperative month. [Time Frame: 6 months after PTx procedure]

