#### **4.12 End of Study Definition**

A participant is considered to have completed the study if he or she has completed all phases of the study including the last visit or the last scheduled procedure shown in the calendar of events or has been discontinued.

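### Investigator-initiated withdrawal can end outcome follow-up before month 6, for reasons that may overlap with surgical failure

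*Combined protocol and SAP*

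**What the plan says.** Investigator-initiated Withdrawal, in Section 4, sets a best-interests test: "The investigator will withdraw a subject whenever continued participation is no longer in the subject's best interests". Examples follow: "Reasons for withdrawing a subject include, but are not limited to, disease progression, the occurrence of an adverse event or a concurrent illness". The list goes on to the subject's own request, noncompliance and uncertainty on the investigator's part. The removal is from the study, not only from the intervention: the reason is recorded and "the date the subject was removed from the study must be documented".

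Section 4.1 uses a single Withdrawn status for two kinds of subject: one who refuses all follow-up, and one who "is taken off study by the local principal investigator". Consent Withdrawal offers a middle course, "Selective consent withdrawal from interventional portion of the study, but agree to continued follow-up of associated clinical outcome information", but only to a subject who is withdrawing consent. Section 4.12 counts as having completed the study a participant who has reached the last visit or "the last scheduled procedure shown in the calendar of events or has been discontinued".

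Other sections depend on long follow-up of patients who are not cured. Under 2.2.3, values that are abnormal at the first visit are measured again, and the operation has failed if the abnormality "persists at or after the 6th postoperative month". Section 2.3.12 counts visits and admissions for persistent hypercalcemia up to 6 months, and 2.3.13 counts repeat operations at 6 to 12 months. Follow-Up Visits schedules laboratory tests, history and complications at 5-14 days and at 6 months.

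Section 6 covers sample size only. It allows for 20% attrition but names no analysis population and gives no rule for withdrawn patients.

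**The concern.** A rule that takes subjects off study for progression or toxicity suits a drug given repeatedly, where it also stops exposure. Here the exposure is over when the operation ends. Withdrawal after surgery can only stop observation.

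The listed reasons may also overlap with what the trial measures. All patients have primary hyperparathyroidism, so disease progression could be read as persistent or worsening disease, which is the subject of 2.2.3. Section 5.2 treats any clinically relevant laboratory deterioration as an adverse event, so a worsening calcium or PTH value could itself be a listed reason. Complications belong to part (iii) of the primary objective.

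If such patients leave before month 6, the failure rate among those still observed is too low. The Protocol Summary describes the trial as open-label, so discretionary removal could also differ by arm and create or hide a difference. Analysis cannot recover outcomes that were never collected.

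**Working it through.** **1. The texts side by side**

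| Question | Withdrawal and status rules | Outcome and visit rules |
|---|---|---|
| May a patient with persistent disease leave before month 6? | Yes, if the investigator judges it in the patient's best interests | 2.2.3 and Follow-Up Visits need values at month 6 |
| Are outcome data kept after withdrawal? | Offered for selective consent withdrawal only | 2.3.12 and 2.3.13 need events to month 6 and beyond |
| How is the patient classified? | Withdrawn, together with those refusing all follow-up (4.1); discontinuation satisfies the completion definition (4.12) | No analysis population in Section 6 |

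The outcomes are not equally exposed. Outcome 2.2.1 is read during surgery and 2.2.2 at days 5-14, so both are largely recorded before a failure could lead to removal. Those mainly at risk are 2.2.3, 2.3.12 and 2.3.13.

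**2. The plan's own attrition figure**

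Section 6 goes from 33 to 40 per group per surgeon: 33 × 1.20 = 39.6, rounded up to 40. The Protocol Summary gives N = 160 in equal groups, so 80 per arm. The allowance is 0.20 × 80 = 16 patients per arm.

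Section 1 puts failure at 5-10%. Expected failures per arm are 80 × 0.05 = 4 to 80 × 0.10 = 8. Every expected failure could therefore be lost without exceeding the planned attrition.

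**3. Effect on the observed failure rate**

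Let p be the true failure rate (5-10%, Section 1) and w the share of failures withdrawn before month 6. The documents do not give w, so it is varied from 25% to 100%. Assume that only completers are analysed and that no patient without failure is withdrawn. Then:

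observed rate = p(1 − w) / (1 − pw)

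| w | p = 10% | p = 5% |
|---|---|---|
| 25% | 0.075/0.975 = 7.7% | 0.0375/0.9875 = 3.8% |
| 50% | 0.050/0.950 = 5.3% | 0.025/0.975 = 2.6% |
| 75% | 0.025/0.925 = 2.7% | 0.0125/0.9625 = 1.3% |
| 100% | 0% | 0% |

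In patients, w = 50% turns 8/80 into 4/76, or 4/80 into 2/78.

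**4. Effect on the comparison when there is no true difference**

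- Half of failures withdrawn in one arm, none in the other: risk ratio 5.26/10 = 0.53 at p = 10%, and 2.56/5 = 0.51 at p = 5%.
- Half withdrawn in both arms: 5.26/5.26 = 1, and 2.56/2.56 = 1. Equal withdrawal lowers both rates but does not create a difference.

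If outcomes continue to be collected, w = 0 and the observed rate equals p.

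**The case against.** Several stronger readings are tempting, and the documents do not support them.

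- **That the investigator must remove every patient with progression or an adverse event.** The obligation depends on the best-interests test, and the reasons are examples. Follow-up is mainly examination, blood tests and history, so the test may seldom be met.
- **That the rule removes only failures and complications.** Concurrent illness, the subject's request, noncompliance and investigator uncertainty are also listed. Section 4.1 dates enrolment from eligibility confirmation, so withdrawal can also precede surgery.
- **That disease progression can only mean persistent hyperparathyroidism.** The term is undefined, and persistence is not the same as progression. Drug-trial wording appears elsewhere in the protocol, so this may be carried-over template text.
- **That safety follow-up simply stops.** Follow-up of Adverse Events keeps events under management for 30 days, or until resolution if related to study treatment, with no exception for withdrawn subjects.
- **That Section 4.12 hides the loss.** The reason and date of withdrawal must be recorded, and Withdrawn remains a separate status.

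It is also fair to say that 2.2.3, 2.3.12, 2.3.13 and Follow-Up Visits show an intention to keep failures under observation, and that both the withdrawn share and the completers-only analysis in the illustration are assumptions.

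These points narrow the concern but do not remove it. Intention in one section does not settle what staff do under another. As written, the withdrawal and status rules point towards ending data collection, and nothing in Section 6 offsets that.

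**Conclusion.** The concern holds in a limited form. The protocol lets a discretionary withdrawal end outcome follow-up after a one-time intervention, for reasons that plausibly overlap with surgical failure, and this conflicts with sections that need the same patients observed to month 6 or later. The exposure falls mainly on 2.2.3 and the later secondary outcomes.

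The size is unknown. On the assumptions shown, a true 10% failure rate could be seen as anything from 7.7% down to 0%, and a true 5% as 3.8% down to 0%. A false difference between arms needs unequal withdrawal. Open-label conduct makes that possible, but the documents do not show that it will happen. The overlap between disease progression and surgical failure remains an inference.

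**What to change.** Reconcile 2.2.3, 4.1, Consent Withdrawal, Investigator-initiated Withdrawal, Follow-Up Visits and 4.12 on what data are collected after withdrawal. The change concerns data only and leaves the investigator's clinical discretion as it is.

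1. In Investigator-initiated Withdrawal, state that outcome and safety data continue to be collected to month 6 unless the patient refuses follow-up.
2. In 4.1, give investigator-initiated withdrawal its own status, separate from full consent withdrawal.
3. In 4.12, do not count a discontinued participant as having completed the study.
4. In Section 6, state that these patients are analysed in their randomised arm, and how outcomes still missing will be handled.

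The day 5-14 and month-6 visits are already scheduled for everyone. The cost is protocol wording and a few more visits or chart checks.

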### **4.10 Lost to Follow-up**

The following actions must be taken if a participant fails to return to the clinic for a required study visit and/or is unable to be reached for follow-up:

- The investigator or designee must make every effort to regain contact and/or reschedule a missed visit with the participant.
- A participant is deemed lost to follow-up if his/her status cannot be obtained after *all* of the following occurs at two consecutive scheduled protocol calendar timepoints:
  - Three telephone calls (at least one day apart) from the study team are unanswered  
**AND**
  - A letter to the participant's last known mailing address goes unanswered.  
**AND**
  - These contact attempts must be documented in the participant's medical record or study file.
- Update OnCore® (follow-up tab and eCRF) when a participant is officially considered lost to follow-up.
- If a subject is considered lost to follow-up, but subsequently contacts the participating site study team, the subject should be considered in follow-up again.

### **4.11 Accrual Suspension and Closure**

The MCW PI facilitates the suspension and closing of accrual in the following manner:

- OnCore® tracks accrual throughout the study.

- If the study must be suspended, OnCore® is updated to a ‘suspended’ status.
- When the accrual number is reached, OnCore® notifies staff of study closure.

#### **4.12 End of Study Definition**

A participant is considered to have completed the study if he or she has completed all phases of the study including the last visit or the last scheduled procedure shown in the calendar of events or has been discontinued.

#### **4.13 Study Discontinuation and Closure**

This study may be temporarily suspended or prematurely terminated if there is sufficient reasonable cause (as determined by the MCW study principal investigator, DSMC, sponsor, and/or IRB). Written notification, documenting the reason for study suspension or termination, will be provided by the suspending or terminating party to study participants, investigator, funding agency, the Investigational New Drug (IND) sponsor and regulatory authorities. If the study is prematurely terminated or suspended, the MCW principal investigator (PI) will promptly inform the MCW Institutional Review Board (IRB) and sponsor and will provide the reason(s) for the termination or suspension. Study participants will be contacted, as applicable, and be informed of changes.

## 5 ADVERSE EVENTS: DEFINITIONS AND REPORTING REQUIREMENTS

### 5.1 Definitions

#### 5.1.1 Adverse Event (AE) and Serious Adverse Events (SAE)

The investigator and his or her team will follow the Medical College of Wisconsin policies related to adverse event reporting. This information may be found on the [Human Research Protection Program website](#).

Serious AE (SAE) means any untoward medical occurrence that at any dose:

- **Death.** Results in death.
- **Life threatening.** Is life threatening (refers to an AE in which the patient was at risk of death at the time of the event. It does not refer to an event which hypothetically might have caused death if it were more severe).
- **Hospitalization.** Requires inpatient hospitalization or prolongation of an existing hospitalization (see clarification in the paragraph below on planned hospitalizations).
- **Disability/incapacity.** Results in persistent or significant disability or incapacity. (Disability is defined as a substantial disruption of a person's ability to conduct normal life functions).
- **Medically important event.** This refers to an AE that may not result in death, be immediately life threatening, or require hospitalization, but may be considered serious when, based on appropriate medical judgment, may jeopardize the patient, require medical or surgical intervention to prevent one of the outcomes listed above, or involves suspected transmission via a medicinal product of an infectious agent. Examples of such medical events include allergic bronchospasm requiring intensive treatment in an emergency room or at home, blood dyscrasias or convulsions that do not result in inpatient hospitalization, or the development of drug dependency or drug abuse; any organism, virus, or infectious particle (e.g., prion protein transmitting transmissible spongiform encephalopathy), pathogenic or nonpathogenic, is considered an infectious agent.

Clarification should be made between a serious AE (SAE) and an AE that is considered severe in intensity (Grade 3 or 4), because the terms serious and severe are NOT synonymous. The general term severe is often used to describe the intensity (severity) of a specific event; the event itself, however, may be of relatively minor medical significance (such as a Grade 3 headache). This is NOT the same as serious, which is based on patient/event outcome or action criteria described above, and is usually associated with events that pose a threat to a patient's life or ability to function. A severe AE (Grade 3 or 4) does not necessarily need to be considered serious. For example, a white blood cell count of  $1000/\text{mm}^3$  to less than  $2000$  is considered Grade 3 (severe) but may not be considered serious. Seriousness (not intensity) serves as a guide for defining regulatory reporting obligations.

### 5.1.2 Unanticipated Problem Involving Risk to Subject or Other (UPIRSO)

The investigator and his or her team will follow the Medical College of Wisconsin policies related to unanticipated problems involving risks to subjects or others. This information may be found on the [Human Research Protection Program website](#).

### 5.1.3 AE Attribution and Grading

#### Adverse Event Grading

Grade	Description
0	No AE (or within normal limits).
1	Mild; asymptomatic or mild symptoms; clinical or diagnostic observations only; intervention not indicated.
2	Moderate; minimal, local or noninvasive intervention (e.g., packing cautery) indicated; limiting age-appropriate instrumental activities of daily living (ADL).
3	Severe or medically significant but not immediately life-threatening; hospitalization or prolongation of hospitalization indicated; disabling; limiting self-care ADL.
4	Life-threatening consequences; urgent intervention indicated.
5	Death related to AE.

#### Adverse Event Attribution

Attribution is an assessment of the relationship between the AE and the medical intervention.

Relationship	Attribution	Description
Unrelated to investigational agent/intervention	Unrelated	The AE is clearly NOT related to the intervention
	Unlikely	The AE is doubtfully related to the intervention
Related to investigational agent/intervention	Possible	The AE may be related to the intervention
	Probable	The AE is likely related to the intervention
	Definite	The AE is clearly related to the intervention

## **Relationship Assessment: In-Depth Definitions**

For all collected AEs, the clinician who examines and evaluates the subject will determine the adverse event's causality based on temporal relationship and his/her clinical judgment. The degree of certainty about causality will be graded using the categories below:

**Definitely Related:** There is clear evidence to suggest a causal relationship, and other possible contributing factors can be ruled out. The clinical event, including an abnormal laboratory test result, occurs in a plausible time relationship to drug administration and cannot be explained by concurrent disease or other drugs or chemicals. The response to withdrawal of the drug (dechallenge) should be clinically plausible. The event must be pharmacologically or phenomenologically definitive, with use of a satisfactory rechallenge procedure if necessary.

**Probably Related:** There is evidence to suggest a causal relationship, and the influence of other factors is unlikely. The clinical event, including an abnormal laboratory test result, occurs within a reasonable time sequence to administration of the drug, is unlikely to be attributed to concurrent disease or other drugs or chemicals, and follows a clinically reasonable response on withdrawal (dechallenge). Rechallenge information is not required to fulfill this definition.

**Possibly Related:** There is some evidence to suggest a causal relationship (e.g., the event occurred within a reasonable time after administration of the trial medication). However, the influence of other factors may have contributed to the event (e.g., the subject's clinical condition, other concomitant events). Although an adverse drug event may rate only as "possibly related" soon after discovery, it can be flagged as requiring more information and later be upgraded to "probably related" or "definitely related," as appropriate.

**Unlikely:** A clinical event, including an abnormal laboratory test result, whose temporal relationship to drug administration makes a causal relationship improbable (e.g., the event did not occur within a reasonable time after administration of the trial medication) and in which other drugs or chemicals or underlying disease provides plausible explanations (e.g., the subject's clinical condition, other concomitant treatments).

**Unrelated:** The AE is completely independent of study drug administration, and/or evidence exists that the event is definitely related to another etiology. There must be an alternative, definitive etiology documented by the clinician.

